#### 9.6 Database Locking and Unlocking

After the review is completed and the established database is confirmed to be correct, the principal investigator, sponsor, DM, and statistician will jointly lock the data. In principle, any changes to the locked database are not allowed. If unlocking is required, the application will be jointly signed and submitted by the principal investigator, DM, statisticians and other personnel. The re-locking of the database should follow the same process as the first locking of the database.

# 9.7 Blinding Verification and Unblinding

Not applicable.

# 10. Statistical Analysis

#### **10.1 Sample Size**

This trial is a phase I clinical trial and does not estimate the sample size.

This trial plans to enroll 31-78 subjects in total:

- ➤ It is expected that the dose escalation trial will enroll 19-42 subjects;
- It is expected that the expansion trial will enroll 12-36 subjects.

# 10.2 Statistical Analysis Set

- ① Screening set: All subjects who signed the ICF. The screening set is used to analyze the number of subjects screened, number of subjects enrolled and number of screening failures.
- ② Safety set (SS): All subjects who are enrolled and have taken the study drug. SS is used for the description of demographic data, description of baseline characteristics, safety analysis and efficacy analysis.
- ③ **DLT analysis set (DS):** All subjects who are enrolled and have taken the study drug, but excluding subjects who receive study drug at a dose less than 75% of the scheduled dose for reasons other than toxicities attributable to study drug during the DLT observation period. DS is used for the analysis and summary of DLT.
- **PK analysis set (PKS):** All subjects who are enrolled, have taken the study drug, have at least one PK data for statistical analysis and have no any protocol deviation (e.g., missed dosing of BB102 tablets) that significantly affects the PK parameters [e.g., area under the concentration-time curve (AUC), Cmax, etc.] during the treatment cycle or dosing period containing blood sampling time point. Whether a subject is included into PKS will be determined case by case on the data review meeting. PKS is used for the analysis of PK parameters.
- (5) **Biomarker analysis set (BS):** All subjects who have at least one biological sample for biomarker analysis in the SS. BS is used for the analysis of relationship between biomarker and efficacy.

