#### 1.4 DLT evaluable subjects

If the dose received by a subject during the DLT observation period is less than 75% of the scheduled dose for reasons other than toxicities attributable to study drug, this subject should not be included into the final DLT analysis of this dose group or the overall groups. If the above situation occurs in any subject, the corresponding dose group needs to enroll one more subject for replacement to ensure the minimum required number of DLT evaluable subjects.

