# **Concomitant Medications**

Concomitant medications include any medications other than the study drug (including prescription drugs, over-the-counter drugs, natural extracts, nutritional supplements and traditional Chinese medicines) used by subjects from the start of first dose to 28 days after the last dose of study treatment. Note: Medications used by subjects at screening will be recorded as medication history.

(1) For the dose escalation trial and expansion trial, the following drugs/therapies will be allowed during the treatment period:

- Bisphosphonates for treating bone metastasis. Note: Bisphosphonate therapy should be administered according to the local medical practice.
- Palliative radiotherapy for relieving pain caused by bone lesion, on the condition that this lesion has existed at the time of enrollment and the investigator clarifies the requirement of palliative radiotherapy does not represent disease progression. Note: As there is currently a lack of data on the interaction between BB102 tablets and radiotherapy, BB102 tablets therapy should be interrupted at 1 day before palliative radiotherapy and throughout the radiotherapy period and be resumed after the acute radiotoxicity recovers to baseline level. Note: Palliative radiotherapy is not allowed during the DLT observation period; if the study drug dose received by a subject during the DLT observation period is less than 75% of the scheduled dose due to use of palli'tive therapy and no DLT occurs, the corresponding dose group needs one more subject for replacement.
- Therapeutic drugs used for AE (dose escalation trial), such as choleretics, but only the non-prohibited medications can be used.
- Preventive drugs and therapeutic drugs used for AE (expansion trial), such as choleretics, but only the non-prohibited medications can be used.
- (2) In the dose escalation trial and expansion trial, the following drugs/therapies will be prohibited during the treatment period:
- Anti-tumor therapies rather than the study drug (including but not limited to chemotherapy, radiotherapy, immunotherapy, anti-tumor biotherapy, etc.), including state-approved Chinese traditional patent drugs with an anti-tumor effect.
- Adjuvants (e.g., preventive leukocyte increasing drugs, antiemetics, etc.) related to anti-tumor therapy (for dose escalation trial only).

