# Statistical Analysis

#### Statistical analysis sets:

① Screening set: All subjects who signed the ICF. The screening set is used to analyze the number of subjects screened, number of subjects enrolled and number of screening failures.

- ② **Safety set (SS):** All subjects who are enrolled and have taken the study drug. SS is used for the description of demographic data, description of baseline characteristics, safety analysis and efficacy analysis.
- **3 DLT analysis set (DS):** All subjects who are enrolled and have taken the study drug, but excluding subjects who receive study drug at a dose less than 75% of the scheduled dose for reasons other than toxicities attributable to study drug during the DLT observation period. DS is used for the analysis and summary of DLT.
- **PK** analysis set (PKS): All subjects who are enrolled, have taken the study drug, have at least one PK data for statistical analysis and have no any protocol deviation (e.g., missed dosing of BB102 tablets) that significantly affects the PK parameters [e.g., area under the concentration-time curve (AUC), Cmax, etc.] during the treatment cycle or dosing period containing blood sampling time point. Whether a subject is included into PKS will be determined case by case on the data review meeting. PKS is used for the analysis of PK parameters.
- **⑤** Biomarker analysis set (BS): All subjects who have at least one biological sample for biomarker analysis in the SS. BS is used for the analysis of relationship between biomarker and efficacy.

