It is planned to enroll 3 subjects to other groups, and the specific dose escalation method is shown in Figure 3. For each dose group, if none of the 3 subjects experiences DLT, the trial will proceed

to the next dose group. If  $\geq 2$  out of the 3 subjects experience DLT, the dose escalation will be discontinued. If 1 of the 3 subjects experiences DLT, 3 additional subjects should be enrolled into this dose group (if none of the 3 newly enrolled subjects experiences DLT, the trial will proceed to the next dose group; If  $\geq 1$  of the 3 newly enrolled subjects experience DLT, dose escalation will be discontinued).

[figure not shown]

Figure 3 The 3+3 escalation diagram in dose escalation trial

The second and third subjects in the 3+3 escalation groups should only be enrolled after the first subject is observed for at least 5 days after dosing (enrolled on or after C1D1 of the first subject). If the previous subject experiences DLT, the sponsor and the investigator need to cautiously judge whether to enroll the next subject based on the safety data; if subsequent subjects have already been enrolled, the enrolled subjects should continue the study treatment (unless these subjects meet the criteria for study treatment discontinuation), with his/her safety data closely monitored.

SMC will decide whether to perform dose escalation or reduction and determine whether to and how to adjust the escalation doses based on the safety, tolerability and/or PK data obtained during the DLT observation period of a certain dose group. Based on the safety, tolerability, PK and efficacy data of a certain group, if the investigator believes that it is necessary to expand the number of subjects of this dose group to further observe the safety and efficacy and obtain PK data, the number of subjects of this dose group may be increased to 4-12 after reaching a consensus with the sponsor through discussion.

To ensure the safety of subjects, the washout time after single-dosing, dosing frequency, cycle setting, and time points of PK sample collection in the subsequent study as well as the design of subsequent escalation doses (e.g., adding dose groups of 520 mg QD and 600 mg QD) may be

timely adjusted based on the previously obtained safety, tolerability, PK parameters [e.g.,  $T_{1/2}$ , drug accumulation after multiple-dosing] and other previously obtained clinical trial data of BB102 tablets.

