## 4.1.1.5 DLT evaluable subjects

If the dose received by a subject during the DLT observation period is less than 75% of the scheduled dose for reasons other than toxicities attributable to study drug, this subject should not be included into the final DLT analysis of this dose group or the overall groups. If the above situation occurs in any subject, the corresponding dose group needs to enroll one more subject for replacement to ensure the minimum required number of DLT evaluable subjects.

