#### **6.2** Concomitant Medications

Concomitant medications include any medications other than the study drug (including prescription drugs, over-the-counter drugs, natural extracts, nutritional supplements and traditional Chinese medicines) used by subjects from the start of first dose to 28 days after the last dose of study treatment. Note: Medications used by subjects at screening will be recorded as medication history.

(1) For the dose escalation trial and expansion trial, the following drugs/therapies will be allowed during the treatment period:

➤ Bisphosphonates for treating bone metastasis. Note: Bisphosphonate therapy should be administered according to the local medical practice.

- ➤ Palliative radiotherapy for relieving pain caused by bone lesion, on the condition that this lesion has existed at the time of enrollment and the investigator clarifies the requirement of palliative radiotherapy does not represent disease progression. Note: As there is currently a lack of data on the interaction between BB102 tablets and radiotherapy, BB102 tablets therapy should be interrupted at 1 day before palliative radiotherapy and throughout the radiotherapy period and be resumed after the acute radiotoxicity recovers to baseline level. Note: Palliative radiotherapy is not allowed during the DLT observation period; if the study drug dose received by a subject during the DLT observation period is less than 75% of the scheduled dose due to use of palliative therapy and no DLT occurs, the corresponding dose group needs one more subject for replacement.
- Therapeutic drugs used for AE (dose escalation trial), such as choleretics, but only the non-prohibited medications can be used.
- Preventive drugs and therapeutic drugs used for AE (expansion trial), such as choleretics, but only the non-prohibited medications can be used.

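### The DLT set excludes subjects under-dosed for non-toxicity reasons even when they had a DLT, so an observed DLT can leave the primary DLT summary

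*Protocol*

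**What the plan says.** Section 10.2 builds the DLT analysis set from all enrolled and treated subjects, "excluding subjects who receive study drug at a dose less than 75% of the scheduled dose for reasons other than toxicities attributable to study drug", within the DLT observation period. The synopsis has the same definition and adds that "DS is used for the analysis and summary of DLT". No other set is named for DLT.

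The rule for DLT-evaluable subjects (Section 4.1.1.5, and item 1.4 of the synopsis) applies the same 75% line. It states that "this subject should not be included into the final DLT analysis of this dose group or the overall groups" and that "the corresponding dose group needs to enroll one more subject for replacement to ensure the minimum required number of DLT evaluable subjects".

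The palliative radiotherapy note in Section 6.2 uses the same line but adds a condition. It first says that "Palliative radiotherapy is not allowed during the DLT observation period". It then asks for a replacement when the dose is "less than 75% of the scheduled dose due to use of palliative therapy and no DLT occurs". The synopsis repeats it: "and no DLT occurs, the corresponding dose group needs one more subject for replacement".

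Section 7.1 makes the classification, severity and frequency of DLT a primary endpoint of the dose escalation trial.

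**The concern.** The general rule tests two things only: how much drug was taken, and why the shortfall arose. It does not ask whether a DLT occurred. Under-dosing is a good reason to set aside a subject without a DLT, because absence of toxicity on too little drug says little about the dose. It is a poor reason to set aside a subject who had a drug-related DLT despite taking less than planned.

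As written, such a subject leaves the DLT summary and is replaced. The certain consequence is an incomplete primary endpoint. The possible consequence is that, if the replacement feeds the 3+3 count, a cohort at 1/3 is read as 0/3.

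This is not a detail left to the SAP. The protocol itself fixes the set and the replacement rule, and an SAP that kept these subjects would contradict it.

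**Working it through.** **Figures in the plan.** The protocol gives no figure for this point. Its enrolment range for dose escalation, 19-42, reproduces from the cohort sizes (1 + 5×3 + 3 = 19; 7×6 = 42) and is not disputed.

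**Where the 75% line falls.** The DLT window is the single dose plus Cycle 1, dosed once daily for 21 days (Section 4.1.1.3).
- Scheduled doses: 1 + 21 = 22, and 0.75 × 22 = 16.5.
- 16 doses: 16/22 = 72.7%, excluded. 17 doses: 17/22 = 77.3%, kept.
- Exclusion therefore needs 6 or more missed doses.

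**Which subjects are exposed.** Section 6.1.2 interrupts dosing when a DLT occurs. A shortfall that follows a DLT is then normally due to toxicity, and the subject stays in the set. Two cases remain:
- (a) A DLT in a subject who has already missed 6 or more doses for other reasons.
- (b) A DLT that appears after the subject stopped for a non-toxicity reason, if the window is read by calendar. With C1D1 on day 6, C1D21 is day 26. AEs are collected to 28 days after the last dose (Section 8.1.2), so even a stop after the single dose on day 1 leaves collection open to day 29, unless new anti-tumor therapy starts first.

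In both cases the event is recorded but excluded from the DLT summary.

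**Single cohort, if the rule enters the 3+3 count.** Take one DLT subject and two clean subjects, with true DLT rate p (assumed) and q = 1 − p. Assume the replacement is evaluable and the SMC does not intervene.
- DLT counted: three more subjects are enrolled and all must be clean, so P(escalate) = q³.
- DLT subject dropped and replaced: P(escalate) = q + p·q³.

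| p | DLT counted | Dropped and replaced |
|---|---|---|
| 0.3 | 0.343 | 0.7 + 0.3×0.343 = 0.803 |
| 0.4 | 0.216 | 0.6 + 0.4×0.216 = 0.686 |
| 0.5 | 0.125 | 0.5 + 0.5×0.125 = 0.563 |

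**On average.** Clean under-dosed subjects are excluded too, so the net effect can go either way. The 3+3 rule gives E(p) = q³ + 3p·q²·q³. At p = 0.3 this is 0.343 + 0.441×0.343 = 0.494. If a share f of DLT subjects and a share u of clean subjects is excluded and replaced, the DLT rate among evaluable subjects is p′ = p(1−f) / [p(1−f) + q(1−u)].
- f = u: p′ = p, so the chance of escalating stays at 0.494.
- f = 5%, u = 10%: p′ = 0.285/0.915 = 0.311, giving 0.471.
- f = 10%, u = 5%: p′ = 0.270/0.935 = 0.289, giving 0.517.

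The values of f and u are assumptions; the protocol gives no frequency.

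**The case against.** The strongest reply is that the gap is thin and the safeguards are real.

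- **Few subjects qualify.** A DLT that comes first leads to a toxicity-related interruption, and Section 4.1.1.4 can make toxicity-driven dose loss a DLT in itself. Case (a) needs many missed doses, although Section 6.1.4 has doses on PK days supervised and lets some missed doses be taken late. Case (b) depends on the window continuing by calendar after dosing stops, which the protocol does not state.
- **Escalation may be untouched.** The 3+3 rule, the MTD definition and the gate to expansion do not name the DLT set, and the last two count all subjects in the group. The SMC decides "based on the safety, tolerability and/or PK data obtained during the DLT observation period of a certain dose group" and meets before the next dose group or when significant toxicity occurs (Section 4.1.1.6).
- **The comparison with Section 6.2 is limited.** That note concerns replacement only, after a therapy it forbids in the window.
- **The present rule treats under-dosed subjects alike whatever their outcome.** The proposed rule does not.

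Most of this stands, and it limits the finding. It does not restore an excluded DLT to the summary. The SMC's judgement does not alter the written definition of the analysis set. A link to escalation also cannot be dismissed, because the replacement clause exists to secure a required number of DLT-evaluable subjects, and the cohort sizes that could set such a number are those of the escalation scheme.

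**Conclusion.** The concern holds. The DLT set and the evaluability rule, each stated in the synopsis and in the main text, can remove an observed DLT from a primary endpoint, and no other text prevents it. The certain effect is limited to the DLT summary and to needless replacement, in rare subjects; the event itself remains in the safety set.

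The effect on escalation is conditional. The change from 0.34 to 0.80 describes a single cohort at an assumed 30% DLT rate, with two clean cohort-mates, the replacement carried into the 3+3 count, and no SMC action. It is not an average effect, and no average bias towards escalation is shown. The note in Section 6.2 shows that the wording is inconsistent; it is not a competing full rule. The change should be made because it protects a primary endpoint at very little cost.

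**What to change.** In four places (synopsis item 1.4, the synopsis definition of the DLT set, Section 4.1.1.5 and Section 10.2), limit exclusion and replacement to subjects below 75% of scheduled dose for non-toxicity reasons who had no DLT in the observation period. State that every subject with a DLT in that period stays in the DLT set whatever dose was received. The four places then agree with the condition already present in Section 6.2.

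This costs a few words, needs no extra data and changes no dose or clinical rule. The price is a more conservative DLT count, because under-dosed subjects are then kept only when they had a DLT. In the formula for p′ above this is f = 0. If under-dosing is independent of DLT, and the DLT set is used for the 3+3 count, the chance of escalating at p = 0.3 falls from 0.494 to:
- 0.472 with 5% under-dosed (p′ = 0.300/0.965 = 0.311);
- 0.449 with 10% (p′ = 0.300/0.930 = 0.323);
- 0.399 with 20% (p′ = 0.300/0.860 = 0.349).

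These percentages are assumed. The case for the change is caution and a complete primary endpoint, not the correction of an average bias.

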# Handling of withdrawal/dropout subjects:

Determination of dropout: All subjects who sign the ICF and are screened to be eligible to enter the trial have the right to withdraw from the trial at any time, regardless of the time and reasons. As long as they do not complete the entire clinical trial observation, they are all dropout subjects. Blood samples and tumor tissue samples already obtained from dropout subjects should be retained, processed, and tested.

Subjects can withdraw from the trial without giving any reasons. While respecting the individual rights of the subjects, the investigator should try his best to understand the reasons for withdrawal, and fill in the reasons for withdrawal in the electronic Case Report Form (eCRF); make all possible efforts to contact the subject (if possible, the investigator should meet the subject in person) to complete the assessment items that can be completed, fill in the end of treatment follow-up record form, and record the time of last medication where possible. For those who withdraw due to an AE, the corresponding AE must be recorded in the eCRF. Subjects should return the remaining study drug to the study site. For subjects who withdraw from the trial due to any reason, their eCRFs should be retained; their last test results should be adopted as the final results; and all data on their efficacy and safety should be analyzed.

All study treatment-related toxicities and SAEs ongoing at the time of study termination must be followed up until relieved, unless in the opinion of the investigator, the improvement of this condition is impossible due to the subject's existing condition.

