#### 4.1.1.3 Escalation method

This study adopts a modified 3+3 escalation design, including accelerated escalation and 3+3 escalation, with 6 fasted dose groups (50 mg QD, 100 mg QD, 160 mg QD, 240 mg QD, 320 mg QD and 420 mg QD) and 1 fed dose group. Note: Before the start of the dose escalation trial, the dosage of the fed dose group cannot be determined temporarily, and an appropriate dose will be selected subsequently by the safety monitoring committee (SMC) according to the previously obtained clinical trial data of BB102 tablets; the trial of the fed dose group can be synchronized with the dose escalation process of the fasted dose groups, and the trial of the fed dose group can also be started after the dose escalation of the fasted dose groups is completed, but the trial of the fed dose group must only be initiated after the equivalent dose is demonstrated to be safe under the fasted condition.

The starting dose group (50 mg QD group) is the accelerated escalation group; other dose groups are 3+3 escalation groups. See Figure 1. All subjects enrolled will firstly receive a single dose for safety observation and PK study, and then undergo a 5-day washout period. Later, subjects will receive multiple-dosing to continue the safety observation and PK study. Multiple-dosing is tentatively scheduled as: once daily in 21-day cycles. After Cycle 1 is finished, a subject can continue to receive the next cycle of treatment if the investigator believes that the subject may benefit from the study treatment.

[figure not shown]

Figure 1 The modified 3+3 escalation design in dose escalation trial

In order to avoid excessive exposure of subjects to ineffective doses, the accelerated escalation group (50 mg QD group) is planned to enroll 1 subject. The method for judging dose escalation is shown in Figure 2. During the DLT observation period (defined as the period from a single dose to the end of Cycle 1 of multiple-dosing), if there is no DLT or grade  $\geq$ 3 drug-related toxicity [defined as an adverse event (AE) definitely/possibly related to the study drug], the enrollment of the next dose group will be started; if any DLT or grade  $\geq$ 3 drug-related toxicity occurs, the group will be converted to the 3+3 escalation mode.

[figure not shown]

Figure 2 The accelerated escalation diagram in dose escalation trial

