#### 4.1.1.4 DLT Definition

DLT observation period is defined as the period from a single dose to the end of Cycle 1 of multiple-dosing.

DLT is defined as an AE definitely/possibly related to the study drug occurring in the DLT observation period (AEs will be graded according to CTCAE v5.0) which meets any of the following criteria:

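### DLT evaluability rests on dose received alone, so a subject lost to observation after 75% of doses but before the end of Cycle 1 counts as having no DLT and is not replaced

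*Protocol*

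**What the plan says.** Section 4.1.1.4 sets the window: "DLT observation period is defined as the period from a single dose to the end of Cycle 1 of multiple-dosing". Within it, Section 4.1.1.3 gives one single dose, after which subjects receive no drug ("and then undergo a 5-day washout period"), then dosing "once daily in 21-day cycles".

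Who counts is settled in two places in the body, and the synopsis repeats both. Section 10.2 takes all treated subjects, "excluding subjects who receive study drug at a dose less than 75% of the scheduled dose for reasons other than toxicities" attributable to the drug. Section 4.1.1.5 begins "If the dose received by a subject during the DLT observation period is less than 75% of the scheduled dose for reasons other than" drug toxicity, and concludes that "this subject should not be included into the final DLT analysis of this dose group or the overall groups". It then requires a replacement subject in that dose group.

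The count drives escalation. Under Section 4.1.1.3, "if none of the 3 subjects experiences DLT, the trial will proceed" to the next dose group.

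**The concern.** The window is defined by time, but evaluability is defined by dose. The two part company for a subject who has taken enough drug and then drops out of observation before Cycle 1 ends. No passage excludes or replaces that subject. With no DLT on record, the subject enters the denominator, and the zero-of-three count, as someone who tolerated the dose.

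The missing days carry information under the protocol's own criteria. The post-dose laboratory sets in the window fall on D5, C1D8, C1D15 and C1D21, and the last is the one at risk. The protocol names the liver as the main target organ in animals, and grade 3 hepatobiliary toxicity can be a DLT. Some criteria in Section 4.1.1.4 also need elapsed time, such as failure to recover within 7 days.

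In a 3+3 design one subject can change the decision. A missed DLT turns 1/3 into 0/3, so the three additional subjects are not enrolled. It turns 2/6 into 1/6, which meets both the MTD definition in Section 4.1.1.3 and the condition in Section 4.1.2 for opening an expansion group.

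**Working it through.** **The plan's own figures.** Section 10.1 gives 19-42 subjects for escalation. The minimum is 1 + 6 × 3 = 19 and the maximum 7 × 6 = 42. With 12-36 in expansion, the total is 31-78. All of these reproduce. The range counts no replacement subjects.

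**Where the 75% test is met.**
- Scheduled doses in the window: 1 + 21 = 22.
- 0.75 × 22 = 16.5, so 17 doses are needed: D1 plus C1D1 to C1D16.
- One dose fewer is 16/22 = 72.7%, which fails. Such a subject, leaving for non-toxicity reasons, is excluded and replaced.
- Counting only the 21 daily doses gives 0.75 × 21 = 15.75, so 16 doses, again C1D16.

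If doses were missed, the threshold comes later and the unseen tail is shorter.

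**Unseen time.** The flow chart gives D1-D5 and then C1D1-C1D21, so the window is 5 + 21 = 26 days. After the C1D16 dose, C1D17-C1D21 remain: 5/26 = 19%.

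**Chance that such a subject had an unseen DLT.** Assume constant hazard over the 26 days and a true DLT rate p. The chance is 1 − (1 − p)^(5/26):
- p = 0.20: 4.2%
- p = 0.30: 6.6%
- p = 0.40: 9.4%

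**Effect on clearing a dose.** A dose clears with 0/3, or with 1/3 followed by 0/3. Let one of the first three subjects leave right after dose 17 and have observed DLT probability p′, while the others have p.
- P(0/3) = (1 − p′)(1 − p)²
- P(1/3) = p′(1 − p)² + 2p(1 − p)(1 − p′)
- P(clear) = P(0/3) + P(1/3) × (1 − p)³

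At p = 0.33:
- Full observation, p′ = 0.33: 0.301 + 0.444 × 0.301 = 0.434.
- Onset uniform over 26 days, p′ = 0.33 × 21/26 = 0.267: 0.329 + 0.444 × 0.301 = 0.463.
- Half of DLTs in the last five days, p′ = 0.165: 0.375 + 0.443 × 0.301 = 0.508.

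| True DLT rate | Full observation | One leaver, uniform onset | One leaver, half of DLTs late |
|---|---|---|---|
| 25% | 0.600 | 0.623 | 0.660 |
| 33% | 0.434 | 0.463 | 0.508 |
| 40% | 0.309 | 0.339 | 0.386 |
| 50% | 0.172 | 0.199 | 0.242 |

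The rise is about 2-3 points with uniform onset and 6-8 points with late onset.

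**The case against.** The strongest reply is that the protocol already covers most early exits.
- A subject below 75% for non-toxicity reasons is excluded and replaced (Section 4.1.1.5).
- A death definitely or possibly related to the drug is a toxicity of grade 4 or above and so a DLT. Stopping drug for 7 days or more because of drug-related toxicity is also a DLT (Section 4.1.1.4).
- A subject who only stops drug has an end-of-treatment visit with laboratory tests within 7 days of the last dose (Section 4.3.4), a 28-day safety visit (Section 4.3.5), and AE collection to 28 days after the last dose or the start of new anti-tumor therapy (Section 8.1.2).
- Section 3.3 asks the investigator to try to contact withdrawn subjects and complete what assessments are possible.
- The SMC reviews the data before each escalation and may look behind the count.

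All of this stands. It confines the gap to withdrawal of consent, loss to follow-up, or death judged unrelated, from C1D16 to the end of Cycle 1. It does not close the gap: no rule tells the SMC to discount a partly observed subject, and none provides for a replacement.

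A reader might also infer that Section 3.3 itself scores such a subject as free of DLT, because for withdrawn subjects "their last test results should be adopted as the final results". That sentence is general dropout handling for test results and does not assign DLT status. The problem arises from the evaluability rule and the escalation count, not from Section 3.3.

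**Conclusion.** The point holds in a narrow form. Evaluability and replacement depend on dose alone, and a subject who drops out of observation after meeting the 75% test is counted as having no DLT. The bias is modest, but it always runs toward declaring a dose tolerable, and it touches a primary endpoint.

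Two stronger readings are tempting. The first is that anyone who leaves or dies before the window closes counts as tolerating the dose. The replacement rule and the DLT definition contradict that. The second is that a cohort could be cleared on only two subjects' worth of information. Treating the leaver as giving no information would raise the chance of clearing at a 33% rate from 0.434 to 0.582, but that subject was observed for 21 of 26 days, and the figures under the actual rule are 0.463 to 0.508.

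The sizes rest on assumptions. The protocol gives no human onset data and no rate of leaving, so the onset patterns are illustrative. The clearing probabilities are conditional on one of the first three subjects leaving immediately after dose 17.

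**What to change.** Change Sections 10.2 and 4.1.1.5 and the two matching synopsis paragraphs together.
- Keep the current 75% exclusion.
- State that every subject who had a DLT, and every subject under-dosed because of drug toxicity, remains in the DLT set. A definition requiring either a DLT, or 75% of doses plus full follow-up, would drop toxicity-limited subjects whom the investigator does not call a DLT. Section 10.2 now keeps them.
- Add that a subject without a DLT who, for reasons other than drug toxicity, was not followed for safety to the end of the DLT observation period is not DLT-evaluable and is replaced under the existing rule. Follow-up may be shown by the C1D21 visit, or by an end-of-treatment or unscheduled safety assessment covering that date.
- Add that one missed assessment in a subject otherwise followed to the end of Cycle 1 does not by itself make the subject non-evaluable.

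The cost is a few sentences and an occasional extra replacement subject through a mechanism that already exists.
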